#### 2.2.1.3 Other efficacy variables

Other efficacy variables will be assessed as specified in Section 8.3.

- ASAS40 response (Week 1, 2, 4, 8, 12, 16, 24, 36, 48)
- Time to ASAS40 response

hisdoci

- Change from Baseline in ASDAS-CRP (Week 1, 2, 4, 8, 12, 16, 24, 36, 48)
- ASDAS status (eg, inactive disease, moderate, high and very high disease activity) (Week 1, iations thereof. 2, 4, 8, 12, 16, 24, 36, 48)
- ASAS20 response (Week 1, 2, 4, 8, 12, 16, 24, 36, 48)
- Time to ASAS20 response ۲
- ASAS5/6 response (Week 4, 8, 12, 16, 24, 36, 48)
- Ankylosing Spondylitis Disease Activity Score major improvement (ASDAS-MI) (Week 1, • extensions 2, 4, 8, 12, 16, 24, 36, 48)
- ASAS partial remission (Week 1, 2, 4, 8, 12, 16, 24, 36, 48)
- Change from Baseline in BASDAI (Week 1, 2, 4, 8, 12, 16, 24, 36, 48) •
- Change from Baseline in BASFI (Week 1, 2, 4, 8, 12, 16, 24, 36, 48) •
- Change from Baseline in Bath Ankylosing Spondylitis Metrology Index (BASMI) (Week 4, • 8, 12, 16, 24, 36, 48)
- Change from Baseline in the Maastricht Ankylosing Spondyntis Enthesitis (MASES) Index (Week 4, 12, 48)
- Physician's Global Assessment of Disease Activity (PhGADA) (Week 4, 8, 12, 16, 24, 36, ۲ 48)
- Change from Baseline in Patient's Global Assessment of Disease Activity (PGADA) (Week ۰ 1, 2, 4, 8, 12, 16, 24, 36, 48)
- Change from Baseline in total and nocturnal spinal pain (Week 1, 2, 4, 8, 12, 16, 24, 36, 48)
- Change from Baseline in the average of Questions 5 and 6 of the BASDAI (Week 1, 2, 4, 8, 12, 16, 24, 36, 48)
- Change from Baseline in Physical Component Summary (PCS) and Mental Component Summary (MCS) of the Short-Form 36-Item Health Survey (SF-36) (Week 4, 12, 16, 24, 36, SUS 48)
- Change from Baseline in Sleep quality (Medical Outcomes Study [MOS]-12 item scale) (Week 4, 12, 46, 24, 36, 48)
- Change from Baseline in Ankylosing Spondylitis Quality of Life (ASQoL) (Week 4, 8, 12, 16, 24, 36, 48)
- Change from Baseline (Week 12, 48) in:
  - Spondyloarthritis Research Consortium of Canada (SPARCC) MRI (SI Joint) score, and
  - Ankylosing Spondylitis spine MRI- activity (ASspiMRI-a) (Berlin modification) score
- Change from Baseline in Hospital Anxiety and Depression Scale Anxiety (HADS-A) and Hospital Anxiety and Depression Scale - Depression (HADS-D) scores (Week 2, 4, 8, 12, 16, 20, 24, 28, 32, 36, 40, 44, 48)

Percentage of subjects with scores below 8 in HADS-A and HADS-D (subjects with normal scores) (Week 2, 4, 8, 12, 16, 20, 24, 28, 32, 36, 40, 44, 48)

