## Double-Blind Period

At Baseline subjects will be randomized in a 1:1:1:1:1 ratio (stratified by region and prior TNF inhibitor exposure) to receive the following blinded study treatment regimens during the Double-Blind Period:

Placebo

Bimekizumab 16mg administered sc Q4W

- Bimekizumab 64mg administered sc Q4W
- Bimekizumab 160mg administered sc Q4W
- Bimekizumab 320mg administered sc Q4W •

The enrollment of TNF inhibitor-experienced subjects will be limited to approximately 30% of the total study population.

Subjects withdrawing early from the study will undergo the Early Termination Visit assessments and will enter the SFU Period. The investigational medicinal product (IMP) will be administered sc in the clinic at Baseline,

The Dose-Blind Period lasts from Week 12 to Week 48. Subjects randomized to bimekizumab 160mg Q4W or bimekizumab 320mg Q4W will remain on their randomized dose and subjects randomized to placebo, bimekizumab 16mg Q4W, and bimekizumab 64mg Q4W, will be rerandomized in a 1:1 fashion to bimekizumab 160mg Q4W or bimekizumab 320mg Q4W. The total duration of treatment is 48 weeks.

During the 36-week Dose-Blind Period, subjects will be evaluated for eligibility to rescue treatment at defined time points. Subjects who do not show an improvement in both PGADA and spinal pain compared to Baseline will be eligible to receive rescue therapy as defined in Section 6.5.

Section 6.5. Safety Follow-Up Visit/Extension study At the completion of the Dose-Blind Period, subjects will be given the opportunity to enter an extension study at Week 48. All subjects who complete the study and do not enter the extension study or who discontinue early, including those withdrawn from study treatment, will have a SFU Visit at 20 weeks after their last dose of IMP.

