#### Determination of sample size 2.4

A total of 285 subjects (57 in each treatment group) are planned to be randomized in this study. The primary efficacy analysis will be based on the Full Analysis Set (FAS). While some randomized subjects may not be in the FAS, it is expected that this number will not impact the following calculations.

The sample size is calculated based on the ASAS40 response data from the Phase 3 studies in subjects with AS treated with secukinumab (MEASURE 1 and 2; Baeten et al, 2015). The ASAS40 response rates at Week 12 were reported to be 40% in both studies for the secukinumab 150mg dose while placebo response rates were 18% (MEASURE 1) and 9% (MEASURE 2).

Based on those ASAS40 response rates and preliminary information on the bimekizumab doseresponse profile, ASAS40 response rates of 40.0%, 36.0%, 20.0%, 15.0%, and 12.0% at the end of a 12-week Treatment Period for bimekizumab 320mg, bimekizumab 160mg, bimekizumab 64mg, bimekizumab 16mg, and placebo have been assumed, respectively. Since the loading dose regimen of MEASURE 1 (iv) was different from MEASURE 2 (sc), the assumption for placebo response was based primarily on MEASURE 2, but with a weighting towards the higher placebo response rate of MEASURE 1.

The sample size for the primary objective of evaluating the dose-response relationship was calculated using a 2-sided test for detecting a linear trend across proportions (Nam, 1987) at a 2sided significance level of 0.05. Assuming 57 subjects in each treatment group, the test for detecting the overall dose response based on ASAS40 response is powered at >99% for the subjects with diagnosis of AS (ie, 57 subjects per group).

The sample size calculations were performed using the software nQuery Advisor® 7.0.

#### DATA ANALYSIS CONSIDERATIONS 3

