#### 6.5 Prohibited medication and rescue medication

Prohibited medications are defined in the protocol (Section 7.8.2).

This doci

Rescue medication will be allowed for some subjects evaluated at weeks 16, 24, and 36. Further details are defined in the protocol (Section 5.1.4). The number and percentage of subjects who used rescue medication will be summarized and listed.

Compliance will be summarized as the number of doses received relative to the number of doses in the received relative to the isions (9)

Percent compliance =  $100 * \frac{\text{Number of doses received}}{\text{Number of doses expected}}$ 

where the total number of expected doses is derived relative to when the subject finishes treatment. If a subject completes treatment 12 doses are expected (Baseline and every 4th week afterwards until Week 44). If a subject discontinues early, then the number of expected doses is based on the time of early discontinuation relative to the dosing visits. If a dose is not completely given at a specific visit (eg, subject only received one injection instead of the two planned injections), then the subject will be considered to have no compliance for the visit. In the formula above it will be counted as no dose received at this visit.

A summary of percent treatment compliance categorized as  $\leq 80\%$  and >80% will be provided by treatment group for the overall treatment period as well as for Double-Blind treatment period. For the Double-Blind treatment period compliance will refer to the first 12 weeks and will be presented by treatment received at baseline. For the overall treatment period, the compliance will be calculated for the following three groups: bimekizumab 160mg, bimekizumab 320mg, and all bimekizumab. Treatment compliance for the bimekizumab 160mg and 320mg group will be calculated for the time the subject receives 160mg or 320mg, eg for a subject who switches from Placebo or bimekizumab 16mg to bimekizumab 160mg at Week 12, the compliance will only be calculated for the time the subject receives bimekizumab 160mg. The all bimekizumab group will consist of all the doses of bimekizumab including bimekizumab 16mg, and will only exclude the time subjects receive Placebo.

A by-subject listing of treatment compliance will be provided, presenting percent compliance and numbers of expected and received doses for the Double-Blind Period and for treatment with any dose of bimekizumab.

## 8

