#### 8.1.2 Primary analysis of the primary efficacy variable

The primary efficacy variable (ASAS40 at Week 12) will be analyzed for all subjects in the FAS.

itations thereof The dose-response relationship between treatment and ASAS40 response will be assessed with an ordered categorical analysis using a non-parametric correlation statistic of Mantel and Haenszel (Mantel and Haenszel, 1959) and modified ridit scores (Bross, 1958) with the corresponding p-value.

The analysis will include geographic region and prior TNF inhibitor exposure (yes/no) as stratification factors. Prior TNF inhibitor exposure will be used as stratification factor as it may have an impact on efficacy. The correlation between dose and ASAS40 response will be evaluated at a two-sided significance level of  $\alpha$ =0.05. This evaluation of dose-response will constitute the primary efficacy analysis.

A table will present the responder rates for placebo, BKZ 16mg, BKZ 64mg, BKZ 160mg, BKZ 320mg, and the correlation statistic of Mantel and Haenszel (ridit score) with the corresponding p-value.

NRI will be used to account for missing data; ie, subjects with a missing ASAS40 score at Week 12 or who discontinued study treatment prior to the Week 12 visit will be considered nonresponders for the primary analysis.

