Subjects in the ESS who discontinue with bimekizumab treatment during the Dose-Blind Period will be treated as missing and categorical/continuous variables will be imputed.

In order to assess the potential bias of the potentially unblinded subjects based on data, the results of the final analysis will be utilized. Results of the ASAS40 response of the rerandomized 320mg and 160mg treatment group at Week 48 will be compared to the potentially unblinded, randomized 320mg and 160mg treatment groups. If the percentage of ASAS40 responders is

comparable as assessed by overlapping 95% confidence intervals, the potential bias is estimated to be at minimum.

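### The SAP concludes that unblinding bias is minimal when two separate 95% confidence intervals overlap, which does not show comparability: a true 10-point difference would pass 83–96% of the time

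*SAP*

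**What the plan says.** SAP Section 8.3 uses the final data to judge whether potential unblinding mattered. It compares Week 48 ASAS40 response in the re-randomized 320 mg and 160 mg groups with that in the "potentially unblinded, randomized 320mg and 160mg treatment groups". If the responder percentages are "comparable as assessed by overlapping 95% confidence intervals, the potential bias is estimated" to be at its minimum. The section gives no margin, no interval or test for the difference, and no method for the confidence intervals. It does not state whether the doses are compared one by one or together.

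The groups are formed as follows. Section 2.4: "A total of 285 subjects (57 in each treatment group) are planned to be randomized in this study". Section 2.3: "The Dose-Blind Period lasts from Week 12 to Week 48". Subjects first assigned to 160 mg or 320 mg stay on that dose, while those "randomized to placebo, bimekizumab 16mg Q4W, and bimekizumab 64mg Q4W, will be" re-randomized 1:1 to 160 mg or 320 mg at Week 12.

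Week 48 ASAS40 is one of the other efficacy variables (Section 2.2.1.3: "ASAS40 response (Week 1, 2, 4, 8, 12, 16, 24, 36, 48"). The primary analysis is at Week 12 (Section 8.1.2: "The primary efficacy variable (ASAS40 at Week 12) will be analyzed for all subjects in the FAS").

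**The concern.** Two intervals can overlap because the groups are alike or because the intervals are wide, and the rule cannot tell these apart. Overlap means only that a difference was not shown, by a criterion much stricter than a 5% test. The SAP nevertheless attaches an affirmative conclusion to that result. The incentive also runs the wrong way: smaller groups and more dropout make minimal bias easier to declare.

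The contrast is not clean either. At Week 48 the originally randomized arms have had 48 weeks on the assigned dose and the re-randomized arms 36. Non-overlap need not mean bias, and overlap could hide bias offset by time on dose.

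At stake is a pre-specified statement about trial integrity. Under Section 4.3.1, treatment codes are released to sponsor personnel other than operational study staff after the Week 12 lock, while investigators and subjects are to stay blind to dose until Week 48. Section 8.3 is where the SAP uses data to ask whether that mattered.

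**Working it through.** The SAP states no operating figure for this rule, so there is none to reproduce.

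**Inputs.** Originally randomized: 57 per dose (Section 2.4), 114 for both doses. Re-randomized: 3 × 57 = 171 (Section 2.3), or 171/2 ≈ 85 per dose. The SAP gives no Week 48 ASAS40 rates. A re-randomized rate of 40–60% is assumed, with the originally randomized rate higher by *d*. No attrition is assumed unless stated.

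**How far apart must the groups be?** Wald intervals stop overlapping when the observed gap exceeds 1.96·√(p(1−p)/n₁) + 1.96·√(p(1−p)/n₂). At p = 0.5:
- Per dose, 57 vs 85: 13.0 + 10.6 = 23.6 points (23.1 at p = 0.4 or 0.6).
- Pooled, 114 vs 171: 9.2 + 7.5 = 16.7 points (16.3 at p = 0.4 or 0.6).
- Per dose with 20% attrition, 46 vs 68: 14.4 + 11.9 = 26.3 points.

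**Implied significance level.** Per dose, 23.6 points divided by the standard error of the difference (16.8/1.96 = 8.56 points) is 2.76, a two-sided level of 0.0058. Full enumeration of the two binomials gives 0.7–0.8% with Wald intervals and 0.3% with exact (Clopper-Pearson) intervals.

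**Probability that the intervals overlap**, so that bias is called minimal. Full enumeration; each range runs over re-randomized rates of 0.4, 0.5 and 0.6:

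| True difference | Per dose, Wald | Per dose, exact | Pooled, Wald and exact |
|---|---|---|---|
| 10 points | 92–94% | 96% | 83–89% |
| 15 points | 78–82% | 86–88% | 52–65% |
| 20 points | 53–63% | 65–72% | 17–33% |

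Per dose, a 20-point difference is therefore flagged only 28–47% of the time. With 20% attrition, a 10-point difference passes 94–97% of the time per dose.

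**Larger differences.** The planned Week 12 effects against placebo are 36 − 12 = 24 points (160 mg) and 40 − 12 = 28 points (320 mg). Per dose, differences of those sizes would be flagged 46–70% and 65–89% of the time across base rates and interval methods.

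**If non-overlap at either dose counts** (both doses equally biased and independent, base rate 50%, Wald): 1 − (1 − 0.066)² = 13% flagged at 10 points, 1 − (1 − 0.183)² = 33% at 15, and 1 − (1 − 0.391)² = 63% at 20.

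**What the data can resolve.** The 95% interval for the difference has half-width 1.96·√(p(1−p)(1/n₁ + 1/n₂)). This is 16.4–16.8 points per dose and 11.6–11.8 pooled. Neither can fit inside ±10 points.

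**The case against.** The strongest objection is about weight. The check governs no primary, secondary or safety inference, no analysis set and no type I error. Dose selection rests on the Week 12 interim, and only one interpretive sentence changes with the result. Procedural safeguards may also be set out in the blinding plan cited in Section 4.3.1, which is not part of the SAP. This stands, and it limits how serious the point is. It does not make overlap evidence of comparability, and nothing else in the SAP repairs the rule.

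Dose-for-dose comparison is also the more natural reading of Section 8.3, so the pooled figures, which supply the lower end of the 83–96% range, may not apply. If so, the rule is weaker, at 92–96%. A third reading, using the treatment-sequence labels of Section 3.1, would leave about 28 subjects (57/2) in each re-randomized sequence and be weaker still.

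The rates rest on an assumed 40–60% response at Week 48 and on planned numbers. That is a fair caveat, but the result is stable: widening the lower of the two rates to 25–65% gives 91–96% per dose and 81–89% pooled for a 10-point difference.

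Finally, the time-on-dose imbalance is a design feature that an interval for the difference would also carry. It calls for a stated caveat, not a different analysis.

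**Conclusion.** The concern holds. Followed exactly, the rule would usually declare bias minimal when a true 10-point difference exists (83–96% across both readings and interval methods). For 15 points the figure is 78–88% per dose and 52–65% pooled. Large differences are often caught, especially pooled, but per dose the rule still misses a 20-point difference more often than not. These figures assume planned group sizes, no attrition and a 40–60% Week 48 rate in the re-randomized group; attrition makes the rule more lenient. The reading (per dose or pooled) and the interval method both move the threshold, and the SAP fixes neither. Reach is limited to the interpretation of Week 48 ASAS40. The text should be changed, but the trial's main conclusion does not depend on it.

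**What to change.** In SAP Section 8.3:
- Replace the overlap rule with the estimated difference in Week 48 ASAS40 (originally randomized minus re-randomized), per dose and pooled, with its 95% confidence interval and a named interval method.
- State that the interval limits what size of bias can be excluded. Expect about ±17 points per dose and ±12 pooled before dropout.
- Delete the automatic conclusion that bias is minimal.
- State that the contrast is confounded with time on the assigned dose (48 versus 36 weeks).

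The cost is one table and two or three sentences, with no new data. The sponsor may have to report that a moderate bias cannot be excluded, which is what the planned numbers allow.

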#### 8.3.1 Bath Ankylosing Spondylitis Metrology Index (BASMI)

un; unereof. ured one thereof. .nt's variations of variation and any extensions of variation and any extension and any extensions of variation and any extension and any extensions of variation and any extensions of variations of v The BASMI characterizes the spinal mobility of a subject with AS and consists of 5 clinical measures to reflect axial status: cervical rotation; tragus-to- wall distance; lateral lumbar flexion; lumbar flexion (modified Schober); intermalleolar distance. Each of the 5 movements is scored according the linear BASMI definition (see bullet points below). The mean of the 5 scores provides the BASMI score. The higher the BASMI score, the more severe is the patient's limitation of movement due to their AS.

BASMI linear definition (S=score, A=assessment):

- Lateral lumbar flexion (mean right/left): S = (21.1 cm A) / 2.1 cm•
- Tragus-to-wall distance (mean right/left): S = (A 8 cm) / 3 cm•
- Lumbar flexion (modified Schober): S = (7.4 cm A)/0.7 cm•
- Intermalleolar distance: S = (124.5 cm A) / 10 cm•
- Cervical rotation (mean right/left):  $S = (89.3^{\circ} A) / 8.5^{\circ}$ ۲

The points above have all the additional condition  $0 \le 10^{\circ}$ .

For cervical rotation, tragus-to-wall distance and **lumbar** flexion, take the mean of the left and right measurements, if both are available. Otherwise, the available measurement will be used.

For the lumbar flexion (modified Schober), values greater than 9.0 cm (Maksymowych, 2006) will be flagged as invalid and treated as if they were missing values. The below imputation rules apply for BASMI.

If 1 or 2 clinical measures for the BASMI are missing at one visit, the missing measure will be imputed by carrying the last observation forward, and the BASMI will be calculated accordingly. If no value is available for the clinical measure before the missing time point, the next observation may be carried backwards. If more than 2 items are missing, the BASMI score will be treated as missing.

#### Physician's Global Assessment of Disease Activity (PhGADA) 8.3.2

The Investigator will assess the overall status of the subject with respect to their AS signs and symptoms and functional capacity (considering both joint and skin components) using an NRS in which 0=very good, asymptomatic and no limitations of normal activities and 10=very poor, very severe symptoms which are intolerable and inability to carry out normal activities.

#### Short Form – 36 Items Health Survey 8.3.30

The SF-36 measures the following 8 health domains as rated by the subjects over the past four This docur weeks: Physical Functioning, role Physical, Bodily Pain, General Health, Vitality, Social Functioning, Role Emotional, and Mental Health. The questionnaire is available in Section 12.8. The classification of the questionnaire items to the health domains is shown in Section 12.9.

The SF-36 PCS and MCS are used to measure the two broad components, or aspects, of healthphysical and mental. PCS and MCS are based on the aggregate of 8 health concepts described

above and all of the eight health domain scales are used to score both components summary measures.

One additional item asks respondents about health change over the past year.

tions thereof The SF-36 will be used using QualityMetric's Health Outcomes™ Scoring Software. The software uses updates 2009 U.S. population norms and applies a Full Missing Score Estimation method as follows:

- A health domain score (except the physical functioning domain) will be estimated provided that at least one non-missing response is available within that domain.
- For the physical functioning domain item response theory will be used to develop a model for estimates of the missing score.
- Regression methods are then applied to estimate the PCS and the MCS on the basis of the • available domains. SUN

#### Medical Outcomes Study (MOS) Sleep Scale 8.3.4

The MOS Sleep Scale is a validated generic self-administered scale measuring specific aspects of sleep. The frequency with which each problem has been experienced during the previous 4 weeks is rated on a 6-point scale ranging from "none of the time" to "all of the time", except sleep quantity, which is reported in hours. All scores are transformed linearly to range from 0 to 100, again with the exception of the sleep quantity subscale, which is scored in hours. Higher scores indicate more of the attribute implied by the scale name (eg, more sleep disturbance, more adequate sleep, or greater sleep quantity). The questionnaire is available in Section 12.10.

The item scores (1, and 3 through 12) are used to derive 7 different scale scores. In addition, the average number of hours slept over the past 4 weeks (Item 2) is used to create a raw and a dichotomized measure of sleep. The scale scores are created by averaging the respective rescaled item scores. Scales with at least 1 item answered can be used to generate a scale score. Items that are left blank (missing data) are not taken into account when calculating the scale scores. Scores represent the average for all items in the scale that the respondent answered. The domains of interest for this study are the Sleep Disturbance and the Sleep Problems Index II domains. The table below describes which items are used for both sleep scales.

#### MQS Sleep Scale Scores Table 8–1:

Scale description (Short name)	Item score	
Sleep disturbance (SLPD4)	1, 3 (R), 7 (R), 8 (R)	
Sleep problems Index II (SLP9)	1, 3 (R), 4, 5 (R), 6 (R), 7 (R), 8 (R), 9 (R), 12	
(R) refers to a reversed item. Prior to averaging, the item score is re-scaled as shown in the following table.		
this doct		

Item numbers	Original response category	Re-coded value (not reversed)	Re-coded value (reversed) N/A valiation - extensions of valiation - extensions of valiation - extensions of valiation - extensions of valiation	reot
1	<1			the.
	1	0		S
	2	25		
	3	50	N/A 101	
	4	75	os	
	5	100	ions	
	>5		ans'	
3, 5, 6, 7, 8, 9, 10, 11	<1		· et	
	1		100	
	2	0	80	
	3	N/A	60	
	4	, till	40	
	5	d olice	20	
	6	R 3Pt	0	
	>6	C xion		
4, 12	<1	. Not		
		8	100	
		20	80	
	3 Ruing	40	60	
	4	60	40	
	5 5	80	20	
	6 201	100	0	
	>6	•		
N/A=not applicable.	$ \begin{array}{c} <1 \\ 1 \\ 2 \\ 3 \\ 4 \\ 5 \\ 6 \\ >6 \\ <1 \\ 1 \\ 2 \\ 3 \\ 4 \\ 5 \\ 6 \\ >6 \\ >6 \\ >6 \\ >6 \\ >6 \\ >6 \\ >6 $	·	•	

Table 8–2: MOS Sleep Scale recoding of items

